## 17.11 Anticoagulation Guidelines

### Anticoagulation Guidelines

**Please note that these guidelines will be reviewed throughout the study by the HeartWare Investigators and possibly revised according to patient experience.**

Anticoagulation should be individualized for each patient. If heparin is used in the post-operative period, begin **low dose heparin** at 10 units/kg/hr on postoperative day one to a target PTT of 40-50 seconds. Prior to initiation of anticoagulation, chest tube drainage should be less than 40 ml/hr for approximately three hours, the hematocrit should be stable without the need for transfusion of blood products and coagulation factors should be approaching normal. Gradually increase the heparin dosage to maintain the aPTT in a range of 50-60 seconds.

The recommended long term oral anticoagulation regimen for the MVAD Pump is a combination of **warfarin** and **acetylsalicylic acid (ASA)**. In general, ASA should be started at a dose between 75 and 150mg/day within 24 hours after implant if there are no postoperative bleeding complications. Check for ASA resistance with a reliable test (e.g. VerifyNow) and adjust ASA mono-therapy accordingly. Other multi drug options include;

- Aggrenox (25 mg ASA plus 200 mg extended release dipyridamole )
- ASA 81 mg plus clopidogrel 75 mg daily

For patients who are aspirin sensitive or otherwise intolerant, clopidogrel at doses of 75-150 mg/day is a viable alternative. A clopidogrel loading dose of 300 mg followed by 75 mg/day is recommended to reduce the lag time in reaching full therapeutic benefit (typically a 3-4 day lag). Warfarin should be started within 4 days post-op and titrated to maintain an INR of 2.0 to 2.5.

[figure not shown]
## 17.12 Download of MVAD® Pump Controller Log Files

The download function allows the clinician to:

- Transfer alarm, trend, and event data from the controller to the monitor.
- Transfer the data from the monitor to a USB flash drive.

### To download log files from the controller to the monitor:

1. Use the monitor data cable to connect the data port (blue) on the controller to the monitor. As soon as the cable is connected, the Data Download  icon in the lower left hand corner of the monitor screen flashes grey to indicate that the download has begun.
2. Wait until the Data Download  icon stops flashing and turns black, and then disconnect the monitor data cable from the controller.

**NOTE:** DO NOT disconnect the controller from the monitor when the Data Download  icon is flashing, as data is being transferred. If the message, **[Log Transfer Not Complete!]** appears, re-connect the controller to the monitor to complete the transfer of data.

### To download log files from the monitor to a USB flash drive:

1. Press the Pump  icon to access the System screen and enter the password.
2. Press **[Setup]** tab.
3. Press **[Patient]** tab.
4. Shortly after disconnecting the data cable, the **[Log Files]** button will appear. Press this button and a list of the patient logs will be displayed.
5. Place a HeartWare Monitor compatible USB memory stick into the USB port on the right side of the monitor.
6. Select the logs to be saved. Press the **[Save to USB]** button.
7. A confirmation screen will appear to affirm selection. If correct, press **[Yes]** button.
8. A **[Download complete]** message will appear when data download is complete. Press **[OK]**.
9. Remove the USB flash drive and email the three files: data, alarm, and events (three separate files) to [[contact]](mailto:[contact]).

## 1.0 PURPOSE

This testing will be conducted at Austrian and Australian sites to assess the flow estimation algorithm of the MVAD pump blood in the clinical setting.

## 2.0 INTRODUCTION

Estimated MVAD Pump blood flow is calculated using motor parameters and the patient's hematocrit. Flow estimation operates at speeds of  $\geq 11000$  RPM. At set speeds of  $< 11000$  RPMs the flow estimation will display as ---.

The valid range of estimated MVAD Pump average blood flow is 0 to 7 L/min. The maximum error is  $- 2.5$  L/min. For the most accurate flow estimation, ensure current hematocrit values are entered for this protocol.

## 3.0 MEASUREMENTS

The table below shows the parameters of interest:

Parameters
Hematocrit (%)
Pump Speed (RPM)
Pump Power (W)
Pump Estimated Flow (LPM)
Pump Measured Flow (LPM)
Pulsatility of Pump Measured Flow
Mean Arterial Pressure (mmHg)
Mean Arterial Pulse Pressure (mmHg)

## 4.0 PROTOCOL

### 4.1 Methodology

1. Implant patient with MVAD Pump per MVAD System IFU.
2. Instrument the patient with following two sensors
  - a. 12 mm Transonic Flow Probe is placed on the outflow graft
  - b. Pressure transducer is inserted into arterial vasculature for measurement of mean arterial pressure. Choice of pressure sensor is based on site preference.
3. Using the MVAD system monitor, ensure the following settings are in place prior to initiating the speed ramp:
  - a. qPulse = OFF
  - b. Suction = ALARM ONLY
  - c. Pump Pressure Algorithm = ENABLED
4. Start/set MVAD pump speed to 8 kRPM. Wait at least 1 minute to achieve hemodynamic stability and then record parameters as indicated in Table 1 of the Appendix.
5. Increase MVAD pump speed by increments of 1 kRPM to 18 kRPM (or the speed that will remain the patient's normal set speed). Wait a period of at least 1 minute in between each speed increase and record parameters as indicated in Table 1 of the Appendix.
6. Once speed ramp is complete, remove all unnecessary

## 5.0 SAMPLING PLAN AND JUSTIFICATIONS

This protocol covers the normal patient operating range. Mean arterial pressure as well as other hemodynamic and echocardiographic parameters may be used to monitor the patient state and ensure appropriate setting of pump speed.

## 6.0 DATA ANALYSIS/ ACCEPTANCE CRITERIA

Pump flow estimation data will be analyzed for accuracy by comparing values to measured pump flow values. Acceptance criteria for this protocol will be if the difference between estimated pump flow and measured pump flow is within the specified tolerance ( $\pm 2.5$  L/min).

**7.0 APPENDIX: DATA COLLECTION TABLE**

In addition to noting the patient's hematocrit, the below table will be used for data collection of parameters of interest.

**Patient Hematocrit:** \_\_\_\_\_

**Table 1. Parameters of Interest**

Set Speed (kRPM)	Power (W)	Est. Flow (L/min)	Meas. Flow (L/min)	Meas. Flow Pulsatility (L/min)	MAP (mmHg)	Mean Arterial Pulse Pressure (mmHg)
8		X				
9		X				
10		X				
11						
12						
13						
14						
15						
16						
17						
18

**Revision History**

Version	Date	Revision Author	Comments
1.0	14MAY2015	██████	Initial Document
2.0	20SEP2017	██████	Updates for final analysis changes

**1 LIST OF ABBREVIATIONS AND DEFINITIONS OF TERMS**

ADE(s)	adverse device effect(s)
AE(s)	adverse event (s)
AHA	American Heart Association
ATC	anatomical therapeutic chemical
BMI	body mass index
BP	blood pressure
bpm	beats per minute
BSA	body surface area
C	Celcius
CEC	Clinical Events Committee
CFB	change from baseline
CFR	code of federal regulations
CI	confidence interval
CIP	Clinical investigation plan
cm	centimeters
CNS	central nervous system
CRF	case report form
CSR	Clinical Study Report
CT	Computed Tomography
CVA	Cerebral Vascular Accident (stroke)
DD	device deficiencies
DMC	Data Monitoring Committee
DSMB	Data Safety Monitoring Board
EU	European Union
F	Fahrenheit
FDA	Food and Drug Administration
g/dL	grams per deciliter
GCP	good clinical practice
HR	heart rate
hr(s)	hour(s)
HVAD	HeartWare ventricular assist device
IBPM	intensive blood pressure management plan
IC	Informed Consent
ICH	International Conference on Harmonisation
ICU	intensive care unit

INTERMACS	Interagency Registry for Mechanically Assisted Circulatory Support
IPD	Important protocol deviations
IRB	institutional review board
ISHLT	International Society of Heart and Lung Transplantation
ITT	intent-to-treat
kg	kilograms
KCCQ	Kansas City Cardiomyopathy Questionnaire
KM	Kaplan-Meier
L/min	liters/ minute
LA	left atrial
LOS	length of stay
LOT	length of operative time
LV	left ventricular
LVAD	left ventricular assist device
LVEDD	left ventricular end diastolic diameter
LVEDV	left ventricular end diastolic volume
LVEF	left ventricular ejection fraction
LVESD	left ventricular end systolic diameter
LVESV	left ventricular end systolic volume
m	meters
MAP	mean arterial pressure
max	maximum
MedDRA	Medical dictionary for regulatory activities
mg	milligram
min	minimum
mL	milliliters
ms	milliseconds
MRS	Modified Rankin Scale
MVAD	miniaturized ventricular assist device
N	number of patients
NI	Non-inferiority
NIH	National Institutes of Health
NIHSS	National Institutes of Health Stroke Scale
NP	Nurse Practitioner
NYHA	New York Heart Association
PA	Physician's Assistant
PCWP	pulmonary capillary wedge pressure
PD	pharmacodynamic

PG	Performance goal
PK	pharmacokinetic
PP	per protocol
PVR	Pulmonary Vascular Resistance
RHC	right heart catheterization
RN	Registered Nurse
RPM	revolutions per minute
RR	respiration rate
RVAD	right ventricular assist device
SADE	serious adverse device effect
SAE	serious adverse event
SAS □	(statistical analysis software)
SD	standard deviation
SOC	system organ class
SOP	standard operating procedures
SVO 2	Mixed Venous Oxygen Saturation
TEAE	treatment-emergent adverse event
TEMP	temperature
TIA	Transient Ischemic Attack
TTD	time to death
UADE	unanticipated adverse device effect
USADE	unanticipated serious adverse device effect
VAD	ventricular assist device
VAS	visual analogue scale
WHO	World Health Organization

## 2 INTRODUCTION

Heart failure is one of the leading causes of death in the developed world. It is estimated that 2-6% of the adults in the world suffer from heart failure with a higher prevalence in industrialized nations. There are up to 15 million cases in the European Union, approximately 5.3 million diagnosed cases in the United States, and up to 300,000 cases in Australia. Overall, 50% of patients with heart failure are dead within four years, while 40% who are hospitalized due to acute heart failure are readmitted or dead within one year. Improvements in medical treatments and longer life expectancies have expanded the potential heart failure patient population, consequently increasing the prevalence of the disease. Cardiac transplantation is currently the most effective therapy for advanced heart failure. However, the lack of available donor organs restricts this form of therapy to just over 3,700 patients/year worldwide, as reported to the International Society for Heart and Lung Transplantation (ISHLT) Transplant Registry.

Over the last decade, bridging to cardiac transplantation with implantable left ventricular assist device (LVAD) systems has gained wider clinical acceptance, and today LVADs are used to extend life expectancy for patients with advanced heart failure who deteriorate while awaiting a donor heart. Approximately 32% of the patients who receive heart transplants are bridged with ventricular assist devices. There are currently several devices approved for bridging to cardiac transplantation in the EU. The use of permanent LVADs as an alternative to transplantation has also been approved. This permanent use is known as destination therapy.

The HeartWare® Miniaturized Ventricular Assist System includes an implantable continuous, axial flow pump (MVAD® Pump) that was designed to provide flows up to 7 L/min in a small device that is both lightweight and simple to use. Due to its small size and mechanical simplicity, the MVAD® Pump may provide benefits not currently available with existing technology that require abdominal pump pockets.

Furthermore, the size of the MVAD® Pump may be suitable for patients who cannot tolerate an abdominal surgical procedure.

### **3 STUDY OBJECTIVES**

This multi-center, prospective, non-randomized, single-arm trial will investigate the safety and performance of the HeartWare® Miniaturized Ventricular Assist Device (MVAD® Pump) system over 24 months in subjects with advanced heart failure. Secondary endpoints include the incidence of bleeding, incidence of major infections (per INTERMACS definitions), time to death, incidence of all device failures and device malfunctions, health status improvement, and functional status improvement. Safety measures will include the frequency and rates of adverse events, both overall and for each specific event, which will be collected throughout MVAD® Pump support.

This is a performance goal based trial concerning the primary endpoint and the first secondary endpoint. The primary endpoint is survival at 6 months (estimated to be 85%) based on a performance goal of 70%, with a one-sided significance level of 0.05. The initial Clinical Study Report (CSR) will be submitted with the 6 month data and will be submitted for CE Mark. The secondary endpoint is survival at 24 months (estimated to be 70%) based on a performance goal of 52.5%, with a one-sided significance level of 0.05. These data will be submitted for long term use labeling.

### **4 STUDY DESIGN**

#### **4.1 General Design**

A summary of the study design is presented here; complete details are provided in the protocol.

This multi-center, prospective, non-randomized, single-arm trial will investigate the safety and performance of the HeartWare MVAD® system over 24 months in patients with advanced heart failure. Subjects who undergo explant will continue to have survival status assessed for 1 year after explant occurred. The study population will be selected from patients with chronic American Heart Association (AHA) Stage D/NYHA Class IIIB/IV heart failure who have failed optimal medical management.

After obtaining informed consent, all patients who meet inclusion/exclusion criteria will enter screening visit. All patients will be hospitalized following the implantation and to be evaluated for discharge based on the standard practice of each investigational site. A total of 60 patients will be enrolled, implanted with the MVAD® pump, and will be followed up for 24 months post implantation. Patients will be trained on managing the MVAD® pump which has been implanted prior to discharge from the hospital. Post implant, each patient will be scheduled to have a follow up visit at months 1, 3, 6, 12, 18, and 24 to assess the safety and performance of the device.

The performance of the MVAD® pump will be measured by the overall survival at 6 months and overall survival at 24 months, both to be presented as simple proportion and to be compared with the performance goal of 70% for 6-month survival and 52.5% for 24-month survival using one-sided tests at the 0.05 significance level. Additional parameters of interest include the incidence of major bleeding (per INTERMACS definition), incidence of major infections (per INTERMACS definition), time to death, incidence of all device failures and device malfunctions per INTERMACS definition, incidence of neurological dysfunction per INTERMACS definition, Health Status improvement, Functional status improvement, length of operative time, length of initial stay, re-hospitalizations, transplantations, and explants. Safety measures will include the frequency and rates of adverse events, overall and for each specific event, which will be collected throughout VAD support.

## **4.2 Discussion of Study Design**

This is a multi-center prospective, non-randomized, single-arm study to assess the clinical safety and performance of the MVAD® pump for the treatment of advance heart failure. A multicenter study allows for scientific validity and generalization of the study findings. Since this is a single group study, the outcome of the study will be compared with the performance goal. A PG refers to a numerical value (point estimate) that is considered sufficient by FDA for use as a comparison for a safety and/or effectiveness endpoint.

## **4.3 Method of Assignment of Patients to Treatment Groups**

In this single arm multi-center study, all patients will be implanted with the HeartWare MVAD® pump system.

#### **4.4 Blinding**

Not applicable.

#### **4.5 Determination of Sample Size**

The primary endpoint is survival at 6 months presented as a simple proportion (binomial rate). The survival rate at 6 months is estimated to be 85%, based on HeartWare's experience with the HVAD. This estimated rate will be compared to a performance goal (70%). A sample of 57 subjects is required to satisfy a one-sided significance level of 0.05 and a power greater than 80% (the lower bound of a one-sided 95% exact binomial confidence interval must exceed 70% for success). Three additional subjects (for a total of 60) will be implanted with the MVAD® pump to address for possible attrition due to lost to follow-up or withdrawal.

The first secondary endpoint is survival at 24 months presented as a simple proportion (binomial rate). The survival rate at 24 months is estimated to be 70%, based on HeartWare's experience with the HVAD. This estimated rate will be compared to a performance goal (52.5%). A sample of 57 subjects is required to satisfy a one-sided significance level of 0.05 and a power greater than 80% (the lower bound of an exact binomial confidence interval must exceed 52.5% for success). Three additional subjects (for a total of 60) will be implanted with the MVAD® pump to address for possible attrition due to lost to follow-up or withdrawal.

### **5 CHANGES IN THE CONDUCT OF THE STUDY OR PLANNED ANALYSES**

#### **5.1 Changes in the Conduct of the Study**

There were no changes in the conduct of the study at the time of preparing this statistical analysis plan.

#### **5.2 Changes from the Analyses Planned in the Protocol/CIP**

Due to the early stop of the protocol, fewer than 15 subjects were enrolled. As such, summary statistics are of little use. Therefore, case studies for each subject enrolled and followed will be presented and summary statistics are no longer planned.

### **6 BASELINE, EFFICACY AND SAFETY EVALUATIONS**

#### **6.1 Schedule of Evaluations**

The assessments to be conducted at each scheduled visit are displayed in the following tables.

**Table 1 Time and Event Schedule – Screening to Month 24**

Event / Assessment	Screening/ Pre-implant 72 hours before Implant	Day 1-3/ During initial Hospitalization	Discharge	Month 1, 3 +/-7 days	Month 6 +14 days	Month 12,18 +/- 14 days	Month 24 +14 days
	Informed Consent	X					
Inclusion/Exclusion	X						
Demographics	X						
Cardiovascular/ Medical history & Hospitalization/ INTERMACS Patient Profile	X						
Subject training (HeartWare MVAD® and BP Management)			X				
Urine Pregnancy Screen	X						
Safety Laboratory Chemistry and Hematology	X	X 		X	X	X	X
Hemodynamic Parameter/ Vital signs 	X	X		X	X	X	X
IBPM & Diary Assessments			X	X	X	X	X
Echocardiogram 	X 			X	X	X	X
Implant Data		X 					
MVAD® Pump Parameters 		X		X	X	X	X
Log File Download			X	X	X	X	X
Driveline Care Assessment			X	X	X	X	X
NYHA Classification	X			X	X	X	X
6-Minute Walk	X			X	X	X	X
NIH Stroke Scale / Modified Rankin Scale 	X			X	X	X	X
Quality of Life Questionnaire (EuroQol EQ-5D-5L)	X			X	X	X	X
Kansas City Cardiomyopathy Questionnaire (KCCQ)	X			X	X	X	X
Concomitant Medications	X	X	X	X	X	X	X
Adverse Events	X	X	X	X	X	X	X

1 Day 3 only      2 Detailed schedules in Section 9.1.5 of CIP 3 Echocardiograms obtained within the 6 months prior to ICF may be used for screening  
 4 Implant=Day 1      5 MVAD® Pump parameters will also be recorded daily post discharge until the patient’s blood pressure is stable as defined in Section 9.1.5.2 and at any subsequent hospitalization      6 In addition obtain MRS and NIHSS at time of stroke and at 12 weeks and 24 weeks post-stroke (+/- 7 days)

**Table 2 Time and Event Schedule – Follow-up after Explant of MVAD® Pump**

Event / Assessment	Explant	Month 1 post explant +/-7 days	Month 6 post explant +/-30 days	Month 12 post explant +/-30 days
Visit Date / Survival Status		X	X	X
Concomitant Medications	X			
Adverse Events	X			

## 6.2 Time Point Algorithms

### 6.2.1 Relative Day

The date the device is implanted will be considered relative day 1, and the day before the device is implanted will be relative day -1. Relative days will be calculated as follows only when the full assessment date is known (i.e., partial dates will have missing relative days):

For days on or after the device is implanted:

Relative Study Day (Rel Day) = Date of Assessment – Date of implant + 1.

For days before the device is implanted:

Relative Study Day (Rel Day) = Date of Assessment – Date of implant.

### 6.2.2 Windows

For the purpose of statistical analysis, visits will be analyzed according to their scheduled time point. No windowing will be done. Unscheduled visits will not be summarized but will be presented in the listings.

## 6.3 Baseline Assessments

Baseline is the last measurement before MVAD® Pump is implanted.

The following baseline assessments will be conducted pre-implant.

- Informed Consent obtained
- Inclusion/Exclusion criteria
- Cardiovascular and general medical history including prior hospitalizations
- Demographics (age, race (where applicable), ethnicity (where applicable), gender, weight, height)
- Hemodynamic parameters
- Echocardiogram parameters
- Vital signs (heart rate [HR], respiration rate [RR], blood pressure [BP], and body temperature [TEMP])
- Clinical Laboratory tests (hematology, chemistry, pregnancy test (where applicable))
- NYHA Classification
- 6-Minute Walk
- NIH Stroke Scale
- Modified Rankin Scale
- Quality of Life Questionnaire (EuroQoL EQ-5D-5L)
- Kansas City Cardiomyopathy Questionnaire (KCCQ)
- INTERMACS Patient Profile
- Adverse Events (pre-implant and post informed consent (IC))
- Concomitant Medications (pre-implant)

## 6.4 Efficacy Variables

### 6.4.1 Primary Efficacy Variable – Overall Survival at 6 months

The primary efficacy variable is survival at 6 months after implant expressed as simple proportion of patients alive on the MVAD® pump divided by endpoint eligible patients. The overall survival at 6 months post implant simple proportion point estimate is  $n/N$ ; where  $N$  is the total number of patients included in the analysis set; and  $n$  is the number of patients alive at Relative Study Day 183, lower bound of the 6 month visit.

Patients who are lost to follow-up or who withdraw consent prior to Relative Study Day 183 will be excluded from both denominator and numerator when computing the simple proportion. Patients with transplants, explants for recovery or exchanges (to a device other than the MVAD® Pump) prior to Relative Study Day 183 will be included in the denominator for this analysis, with status identified at time of procedure. If there are any patients who are eligible for analysis but for whom the primary endpoint cannot be assessed, they will be excluded from both denominator and numerator for this analysis.

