### 12.2 Analysis Populations

The Intent-to-Treat (ITT) subject population will include all enrolled subjects intended to receive the MVAD pump at the time of skin incision.

The Per-Protocol (PP) subject population will include all ITT subjects who were implanted with the MVAD pump .

The primary analysis population is the ITT population. All primary and secondary analyses will be performed on the ITT and PP populations.

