### 12.3 Primary Endpoint and Hypothesis

The primary endpoint is survival at 6 months presented as a simple proportion (subjects alive on the MVAD pump divided by endpoint eligible subjects). Transplants, explants for recovery and exchanges (to a device other than the MVAD Pump) prior to 6 month follow-up will be eligible for endpoint analysis (with survival status identified at the time of the procedure). Survival failure is associated with events (death) on the MVAD Pump. The survival incidence at 6 months is estimated to be 85%, based on HeartWare's experience with the HVAD. This estimate will be compared to a performance goal (PG1). The null and alternative hypotheses are provided below:

$$H_0: \pi_{MVAD1} \leq PG_1$$

$$H_A: \pi_{MVAD1} > PG_1$$

$\pi_{MVAD1}$  is the estimated proportion of survival in the treatment group. The performance goal at 6 months is 70%. Success is achieved if the lower bound of the one-sided 95% exact binomial confidence interval exceeds the performance goal.

A sample of 57 subjects is required to satisfy a one-sided significance level of 0.05 and power greater than 80% (sample size determined using SAS 9.2). Three additional subjects (for a total of 60) will be enrolled to address for possible attrition due to lost to follow-up or withdrawal.

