### 7.3 Handling of Dropouts or Missing Data

Patients who are lost to follow-up or who withdraw consent prior to specified relative day will be excluded from both denominator and numerator when computing the simple proportion for the primary endpoint (survival at 6 months) and the first secondary endpoint (survival at 24 months). Patients who are lost to follow-up or who withdraw consent will, however, be eligible for the overall survival analysis.

Transplants, explants for recovery and exchanges (to a device other than the MVAD® Pump) will be eligible for survival analysis with their survival status identified at the time of the

procedure. Death with the MVAD® pump in place is the only event that will be considered a failure.

Patient-years and follow-up time are based on database-driven known time on MVAD® support (including post-exchange time). If a patient is on LVAD support at last known follow-up and a later date of death exists, the date of death must be considered the last follow-up for that patient. The patient is known to be alive and assumed to be on MVAD® support up to the date of death.

If a partial date is reported where the day is missing, then the day will be imputed as the first day of the month unless the month is the same month as the device is implanted then the day will be that of implantation with the month and year remaining the same. If a partial date is reported where the month is missing, then the month will be imputed to January unless the year is the same year as the device is implanted then the month will be that of implantation with the year remaining the same. If a partial date where both the day and month is missing, follow details as stated previously.

Missing data for other parameters will not be imputed for analysis unless defined in Section 6. Censoring for the efficacy endpoints is discussed in Sections 6.4.3.1. Missing adverse event dates will be imputed using partial date imputation rules as previously described in this Section.

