### **8.3.2 Intent-to-Treat (ITT) Population**

All patients who enroll in the study (i.e., have signed informed consent) and who undergo anesthesia for implantation will be included in this analysis set. This population will be the primary analysis population.

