### 8.7.1 Analysis of Primary Efficacy Variable – Overall Survival at 6 Months

The primary endpoint is survival at 6 months presented as a simple proportion (subjects alive on the MVAD® pump divided by endpoint eligible subjects). Transplants, explants for recovery and exchanges (to a device other than the MVAD® Pump) prior to 6 month follow-up will be eligible for endpoint analysis (with survival status identified at the time of the procedure). Trial failure is associated with events (death) on the MVAD® Pump. The survival incidence at 6 months is estimated to be 85%, based on HeartWare's experience with the HVAD. This estimate will be compared to a performance goal (PG1). The null and alternative hypotheses are provided below:

$$H_0: \pi_{MVAD1} \leq PG_1$$

$$H_A: \pi_{MVAD1} > PG_1$$

$\pi_{MVAD1}$  is the estimated proportion of survival in the treatment group. The performance goal at 6 months is 70%. Success is achieved if the lower bound of the one-sided 95% exact binomial confidence interval exceeds the performance goal.

A summary table will include number of patients alive and number of patients dead by study day 183 (the lower bound of the 6 month visit), the proportion for overall survival at 6 months, and the associated lower and the upper 90% exact binominal confidence intervals.

Sensitivity analysis will be performed to assess the impact of the missing data (See Section 8.7.5.1).

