## 11.4 APPENDIX 4: STATISTICAL ANALYSIS AND PROGRAMMING DETAILS

Exact binomial confidence intervals:

- *Make sure the outcome variable is coded properly since BINOMIAL option computes the binomial proportion and confidence limits for the first level of the variable. For example, if outcome is coded 'alive vs dead' the output will have test statistics and confidence limits for survival. If the outcome is coded 'death vs survival', then output will have test statistics and confidence limits for the mortality.*
- *Make sure appropriate alpha is specified since the procedure always produces 2sided confidence limits.*
  - *To obtain 1-sided 95% confidence limits, specify alpha=0.10*
  - *To obtain 2-sided 95% confidence limits, specify alpha=0.05*

*The following is example syntax of SAS code to produce the 2-sided 90% exact binomial confidence intervals.*

```
PROC FREQ DATA=sur6;
  WEIGHT n;
  TABLE outcome / BINOMIAL ALPHA=0.10;
  EXACT BINOMIAL;
  OUTPUT OUT out=bio BIN;
Run;
```

*Where n is total number of patients with outcome of alive and total number of patients with outcome of dead at 6 months. Outcome = Alive or Dead*

*For hypothesis of primary endpoint,*

```
Data result; Set
  bio;
  If round(XL_BIN, 0.01) > 0.70 then NI='Pass'; else NI='Fail';
Run;
```

*For hypothesis of secondary endpoint,*

```
Data result; Set
  bio;
  If round(XL_BIN, 0.01) > 0.52.5 then NI='Pass'; else
NI='Fail';
Run;
```

Kaplan-Meier (KM) Survival Analysis:

*The SAS procedure LIFETEST will be used for Kaplan-Meier survival analysis.*

- *Censored = 1 for all patients survived, patients with transplant or explant, patients discontinued without event of death or lost to follow-up*
- *Censored = 0 for all patients died.*

*The following code will be used:*

```
ods listing close;  
ods output CensoredSummary=censor quartiles = _qt;  
PROC LIFETEST DATA = surv TIMELIM=n;  
TIME surdays*censored(1); run; ods  
listing; ods output close;
```

- *Option TIMELIM is the maximum observation period*
- *surdays= number of days survived post implant*
- *dataset censor contains number of patients censored for this analysis*
- *data \_qt contains KM 25% quartile, median, and 75% quartile estimates of time to death*

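### Could the SAP drop from the survival result an ITT patient who dies before the pump is implanted?

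*SAP*

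**What the plan says.** **Who is in the primary population.** SAP 8.3.2 takes consenting patients "who undergo anesthesia for implantation will be included in this analysis set". Protocol 12.2 takes "all enrolled subjects intended to receive the MVAD pump at the time of skin incision". Neither requires an implant. The per-protocol set is the part of ITT that received the pump.

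**How the proportion is formed.** In SAP 6.4.1 the denominator N "is the total number of patients included in the analysis set", and the numerator is those alive at Relative Study Day 183. The results table in SAP 8.7.1 gives "number of patients alive and number of patients dead by study day 183". Appendix 4 codes "Outcome = Alive or Dead". SAP 6.4.2 and 8.7.2 repeat this for 24 months with day 730.

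**What counts as failure.** SAP 7.3 says that death with the "pump in place is the only event that will be considered a failure". Protocol 12.3 has "Survival failure is associated with events (death) on the MVAD Pump", and SAP 8.7.1 says much the same.

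**What is left out.** SAP 6.4.1 says of patients "eligible for analysis but for whom the primary endpoint cannot be assessed, they will be excluded from both denominator and numerator for this analysis".

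**Related rules.** Relative Study Day (SAP 6.2.1) and time to death (SAP 6.4.3.1) both start at implant, although SAP 8.7.3.1 runs time to death on ITT. The missing-as-failure analysis covers implanted patients in SAP 8.7.5.1 but any subject in protocol 12.8.

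**What is still planned.** SAP 5.2 (version 2.0) records an early stop with fewer than 15 subjects enrolled. It replaces summary statistics with a case study of each subject enrolled and followed.

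**The concern.** A patient who dies after anesthesia or incision but before implant is in ITT, has no implant date and does not die on a pump. Day 183 is therefore undefined for this patient, and the death does not meet the SAP 7.3 description of a failure. Someone applying those rules literally could call the endpoint unassessable and remove the patient from numerator and denominator. The SAP's sensitivity analysis would not bring the patient back, because it is restricted to implanted patients.

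At stake would be an ITT survival figure that omits deaths during the implant procedure. That raises the estimate, moves ITT towards the per-protocol result, and could turn a narrow failure against the performance goal into a success. The time-to-death analysis has a related gap: it is to be run on ITT but has no start date for this patient.

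**Working it through.** **1. Reproduce the plan's own figure.** Inputs (SAP 4.5, 8.7.1 and 8.7.2): one-sided 0.05; goals 70% and 52.5%; assumed survival 85% and 70%; 57 evaluable subjects. Success means that the exact lower bound L exceeds the goal. With x alive of n, L is the 5th percentile of a Beta(x, n − x + 1) distribution.

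- 6 months, n = 57: 45 alive gives 0.6813 and 46 gives 0.7008, so 46 are needed. P(Bin(57, 0.70) ≥ 46) = 0.0486; power P(Bin(57, 0.85) ≥ 46) = 0.862.
- 24 months, n = 57: 36 alive gives 0.5143 and 37 gives 0.5322, so 37 are needed. P(Bin(57, 0.525) ≥ 37) = 0.0397; power P(Bin(57, 0.70) ≥ 37) = 0.837.

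The stated 57 with power above 80% is confirmed for both endpoints.

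**2. Classify the death under the text.**

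| Rule | Applied to a pre-implant ITT death |
|---|---|
| Denominator, SAP 6.4.1 | In the analysis set, so in N |
| Numerator, SAP 6.4.1 | Not alive, so not in n |
| Table, SAP 8.7.1 | Dead |
| Program, Appendix 4 | Outcome is dead; the Kaplan-Meier coding treats every patient who died as an event |
| Exclusion clause, SAP 6.4.1 | Concerns an unknown outcome; this one is known |
| Failure sentences, SAP 7.3 and 8.7.1, protocol 12.3 | Do not cover this death |

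The failure sentence in SAP 7.3 comes straight after the rule for transplants, explants and exchanges. Its evident purpose is to separate death on support from those exits. The arithmetic definition of the endpoint scores the patient as not alive.

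**3. Size if the death were dropped anyway.** Protocol 7.1 continues screening until 60 are implanted, and SAP 4.5 also speaks of 60 implanted. On that reading a pre-implant death comes on top of 60.

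| Case | 6 months | 24 months |
|---|---|---|
| Dropped, N = 60 | 48 fails (0.6962); 49 passes (0.7148) | 38 fails (0.5193); 39 passes (0.5364) |
| One counted, N = 61 | 48 fails (0.6827); 49 passes (0.7008) | 38 fails (0.5098); 39 passes (0.5265) |
| Two counted, N = 62 | 49 fails (0.6874) | 39 fails (0.5170) |

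One such death changes no verdict; two can. Protocol 12.3 and 12.4 speak of 60 enrolled. If ITT totals 60, one is enough: 48/59 passes (0.7103) and 48/60 fails (0.6962); at 24 months 38/59 passes (0.5292) and 38/60 fails (0.5193).

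**4. Error rate.** The documents give no pre-implant death rate q, so q is assumed over a range. True ITT survival is set at 70%, so survival among implanted patients is 0.70/(1 − q). With 60 implanted, dropping gives P(Bin(60, 0.70/(1 − q)) ≥ 49). Counting averages over the number of pre-implant deaths k, a negative binomial count up to the 60th implant. With ITT fixed at 60, dropping averages over k ~ Bin(60, q).

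| Assumed q | 60 implanted: dropped | 60 implanted: counted | ITT 60: dropped | ITT 60: counted |
|---|---|---|---|---|
| 0.5% | 3.4% | 3.3% | 3.5% | 2.9% |
| 1% | 3.8% | 3.5% | 4.2% | 2.9% |
| 2% | 4.9% | 3.9% | 5.8% | 2.9% |
| 3% | 6.3% | 4.0% | 7.7% | 2.9% |
| 5% | 10.1% | 4.0% | 12.1% | 2.9% |

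Dropping exceeds the nominal 5% only above a q of about 2.1% (60 implanted) or 1.5% (ITT 60).

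**5. What is still to be produced.** Under SAP 5.2, neither proportion, no Kaplan-Meier summary and no sensitivity analysis remains planned. With fewer than 15 enrolled, the calculations at 60 describe the original design only.

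**The case for a change.** The strongest reply is that a plan should not depend on a sensible reader. Several sentences tie failure to death on the pump, day 183 has no meaning without an implant, and the exclusion clause is broad. Two mismatches do not depend on interpretation:

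- SAP 8.7.5.1 narrows the protocol's missing-as-failure rule to implanted patients, and SAP 5.2 does not list this as a change.
- Time to death cannot be computed from implant for this patient, yet it is assigned to ITT.

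Both stand. The failure sentences would also be clearer if they mentioned deaths before implant.

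The program in Appendix 4 adds a further point. It rounds the bound to two decimals before comparing it with 0.70. Under that line 49/61 (0.7008) becomes 0.70 and fails, so one counted death would matter even with 60 implanted. But the same line would also fail 46/57, which the success rule in SAP 8.7.1 passes. That is a question about rounding, not about pre-implant deaths.

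Finally, the case studies cover subjects enrolled and followed, and a patient who died before implant was arguably never followed. This is the only point that could still affect output. The patient counts as enrolled by consent (SAP 8.3.1). Protocol 9.5 has every subject death documented in the eCRF, and protocol 14.3.1 has it reported to the sponsor within 24 hours. A team writing up so few cases would include such a death.

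**Conclusion.** No change follows. The proportions as defined already count a pre-implant ITT death as not alive, and reading it as unassessable is strained. Under the original design and the stated success rule, one such death on top of 60 implanted changes no verdict. Two such deaths, or one within an ITT total of 60, could matter at the threshold. Inflation above 5% needs an assumed pre-implant death rate of roughly 1.5% to 2.1% or more, which nothing in the documents supports or rules out.

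The mismatch over missing-as-failure and the implant-based start of time to death are genuine loose ends. Correcting them now would alter no planned result, because the analyses they govern have been withdrawn. Rewording the failure sentence in the protocol would also require an amendment (protocol 16.6) for a trial that has stopped early. Whether a never-implanted patient receives a case study is a detail the analysts can be expected to settle sensibly. This conclusion rests on SAP 5.2 being carried out as written; if the survival analyses were reinstated, the two loose ends would be worth closing.
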